9.6 Data Analyses

Overall analysis approach: Preliminary analysis will be performed to confirm that key data variables are clean and complete in prepared datasets. Baseline patient characteristics will be compared between intervention groups to assess whether important characteristics were evenly distributed during randomization. General analytic approaches will include estimation of odds ratios and risk differences plus chi-square tests for categorical variables compared across groups, rates of change with confidence intervals plus McNemar's test for categorical variables compared pre/post-intervention within groups, and t-tests and multiple regression for comparing continuous variables between groups. Secondary analyses will use random-intercept-random-slope mixed effects models for all repeated measures over time, with linear splines used to estimate initial improvements, subsequent maintenance, and possible eventual backsliding.

The principal analysis will use intent-to-treat methods in which all observations will be included for individuals based on initial group assignment, regardless of adherence to the treatment protocol. As a secondary analytic method, we will also perform as-treated analyses with those who attend at least 2/3

of weekly group sessions (8/12). We recognize the challenge of missing data in assessing clinical trial outcomes. We will take extensive steps to limit missing data. Our team has extensive experience in study retention; in our SUCCEED T2DM study, outcome assessment was completed in 97% of participants at 12 weeks. For our primary mechanism measure, eating in response to cravings using EMA, data can be obtained even for persons who move or have to travel. Finally, we will employ mixed-effects models and multiple imputation methods to address missing data if there is still a substantial amount.

For each of these measures, our primary analysis will be comparison of changes from baseline to follow-up time points between groups (see overall analysis approach above). We will also assess changes from baseline to follow-up within each group to help assess the potential effect of each intervention arm on these measures. We will also test for preliminary evidence that each of these proposed mechanisms is associated with dietary adherence. Dietary adherence will be measured two ways: (1) proportion of blood ketone measures $\geq 0.3\text{mmol/L}$; (2) proportion of kcal from carbohydrate, using 24-hour diet recall. Each of our mechanism measures are continuous variables. We will therefore assess correlations between each of the mechanism measures and the dietary adherence measures, using linear regression. Finally, we will perform initial analysis of whether there are differences in two important clinical outcomes between intervention groups: HbA1c (to examine glycemic control) and weight. These clinical outcomes should result from our intermediate behavioral outcome of improved dietary adherence. We do not expect to have adequate sample-size in either phase of this study to address this question, but believe that preliminary assessment of these outcomes should be performed in case there are dramatic differences between groups even with limited sample size.

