In our theoretical model, mindfulness training directed at eating behavior strengthens the ability to tolerate negative states (e.g., cravings for foods incompatible with one’s dietary goals) without enacting maladaptive automatic behaviors (e.g., eating in response to craving), providing a potentially powerful tool for facilitating healthy eating behavior. Given the relations above, we focus on cravings as a primary mechanism for overeating. Our intervention choice, mindfulness, may have the unique ability to help people tolerate cravings and reduce compulsive eating, as our pilot data suggests.

Mindfulness training can also bolster adaptive stress management, and thereby holds the potential to reduce stress-eating, which is associated with poorer metabolic health. . People who report stress-eating may be more vulnerable to developing obesity and metabolic syndrome.¹⁸ Mindfulness is associated with lower stress-eating in people with diabetes, cross-sectionally.⁸ Our mindfulness-based intervention will include MBSR-based stress management components and Mindfulness Based Eating Awareness Training,¹⁹ which, taken together, act on stress-eating behavior, as well as eating in response to any negative emotions (emotional eating). Improving stress management skills may also directly influence blood glucose levels in T2DM via improvements in maladaptive neuroendocrine responses, as stress hormone responses counteract insulin thereby increasing blood glucose levels..^{20,21} Strengthening adaptive coping responses to stress may also facilitate health behavior such as adhering to medication, diet, and exercise regimens.^{22,23}

There are important new challenges in optimizing mindfulness-based interventions for diet change. This proposal builds on our group’s study of the effects of including mindfulness-based eating and stress management to achieve weight loss and improve metabolic parameters in persons with obesity, but without T2DM (SHINE). While we found evidence of benefits in weight, lipids, and fasting

glucose, we also found variability in participant outcomes by teacher that highlights the need to further optimize the intervention manual/approach.

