3. STUDY DESIGN

This is a two-phase study. Both phases will use a randomized, controlled trial design. After pilot testing in the first phase, the second phase will include employing an adaptive intervention design in the post-treatment phase to test optimization of the maintenance intervention (i.e. assigning maintenance intensity/dose based on how a participant is doing).

We will use ecological momentary assessment (EMA) methods to measure eating in response to difficult emotions and/or food cravings. In the R61 phase, we will ensure this measure is appropriate for further testing and assess the impact of the MBI components on our hypothesized behavioral mechanisms in N=60 community-dwelling adults with T2DM. We plan 3 waves of 20 persons each with 12 weekly sessions followed by 3 monthly maintenance sessions, to be held at UCSF Osher Center for Integrative medicine. All participants will attend an in-person group course providing education on basic behavioral strategies for diet and physical activity. Participants will be randomized (1:1 ratio) to receive this education alone (Ed) or this same material with added MBI components (Ed+MBI). We will also pilot test two levels of intensity of maintenance phase intervention (monthly group meetings alone or supplemented by individualized attention) to prepare them for R33 testing. Assessments will be done at 0, 3 and 6 months. Study participation lasts approximately 8 months per participant. The R61 phase of the study is 2 years total.

We plan an R33 phase trial in which 120 persons with T2DM will be randomized (using a 1:2 ratio) to Ed or Ed+MBI conditions and followed for 12 months, including a 9-month maintenance phase. We will test the robustness of the effect of MBI components on our proposed behavioral mechanisms, and on dietary adherence, as well as preliminary effect sizes on weight and glycemic control. We will use an innovative adaptive intervention design to optimize maintenance phase intensity, which we believe may be key to augment the MBI effects. For this phase, assessments will be conducted at 0, 3, 6 and 12 months, with study participation lasting approximately 14 months per participant, and the entire r33 phase lasting 3 years.

In both phases, randomization will be done using blocked randomization to ensure approximately equal group sizes, with randomly selected block sizes and will be stratified by BMI (below and above

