5. STUDY INTERVENTIONS

5.1 Interventions, Administration, and Duration

All participants will attend 12-weekly study intervention classes based on their random assignment: either Education alone (Ed) or Education+Mindfulness (Ed+MBI). Study groups will be held at the UCSF Osher Center for Integrative Medicine. Both groups will learn and follow a carbohydrate-restricted (CR) diet for T2DM, and will participate in maintenance phase activities. If assigned to Ed+MBI, they will also learn and practice mindfulness-based skills.

Maintenance phase: In the R61 phase, we will pilot test two levels of intensity of maintenance phase intervention (monthly group meetings alone or supplemented by individualized attention) to prepare them for R33 testing.

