9.2 Sample Size and Randomization

Target sample size: 180; 60 participants in the first/R61 phase. 120 in the second/R33 phase.

Our primary hypothesized mechanism is change in frequency of eating in response to cravings. Based on preliminary data, we expect that participants will report that on average, they have eaten in response to cravings on 50% of days on EMA measures at baseline (SD 11%). Our key concern is whether the Ed+MBI group has a significant decrease in days of eating in response to cravings. With N=30 persons in each arm, we will be able to detect a statistically significant decrease with 80% power (alpha=.05), if the group experiences eating in response to cravings on 44% of days or less. We will also test whether there are differences in decreases in cravings between groups.

Based on typical diet interventions for obese persons, we estimate that this will decrease to 30% of days in the Ed group, and 20% of days in the Ed+MBI group, for a mean difference of 10% (SD of 11%). With 30 people in each arm, this will provide us with a power of 80% to detect a statistically significant difference, using a two-tailed test, alpha=.05. For this phase, in which we are screening for evidence of effect on the proposed mechanism, we believe that a one-sided test, corresponding the hypothesis that the Ed+MBI group will have a greater effect on craving related eating than Ed alone, we will have 88% power. Note that we are not accounting for potential drop-outs in the analysis. We

anticipate that almost everyone will get through at least 4 weeks of intervention, which will provide initial data that can be used on all participants. In our pilot study of persons with T2DM and carbohydrate restricted diets, 94% completed the full 13 session program. Even if there is 20% dropout with no usable data, we will have 80% power to detect a statistically significant difference between groups in craving related eating, using a one-sided test.

Though of lesser concern at this early stage, we aim to test whether our hypothesized mechanisms are correlated with dietary adherence measures and will use linear regression. Using our overall sample of N=60, we will have greater than 80% power to detect a significant correlation if the true correlation coefficient (r) is .43 or greater. If we look just at the Ed+MBI group, we will have 80% power to detect a significant correlation if the true correlation coefficient (r) is .53 or greater.

Treatment Assignment Procedures

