Participants will be randomized in a 1:1 fashion to one of two study groups (Ed or Ed+MBI), using block sizes of 4-6, and stratifying by BMI (above and below BMI of 25). We do not have a sample size goal for each stratum, but we want to ensure that the two arms have approximately equal numbers of normal weight participants.

Randomization to intervention group and maintenance phase track will be done via the Salesforce database. The randomization table will be programmed by a database manager, who is not otherwise involved in any enrollment or other participant procedures. Randomization will be done via the Project Director, [name], who will not have access to the randomization table. When a participant ID number is entered into the database by study staff, a group assignment is revealed. This provides a computerized group assignment that cannot be altered by study staff and the group assigned is immediately recorded in the study database.

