9.5 Outcomes

9.5.1 Primary Outcome

Primary mechanistic outcome(s): Our primary hypothesized mechanism is reduction in **frequency of eating in response to cravings** as a result of enhanced ability to address food cravings with mindfulness training. Our key measure of this mechanism is frequency of eating in response to cravings using ecological momentary assessment (EMA). This outcome will be measured at baseline, mid-intervention (approximately weeks 7, 13, and 19) and at final follow-up/end of study (week 26).

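### Section 9.6 does not fix the primary between-arm model, its covariates, its time point or its sidedness; one baseline-adjusted regression at one stated time would settle all four at almost no cost.

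*Combined protocol and SAP*

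**What the plan says.** - **Contrast (9.6).** For each mechanism measure, "our primary analysis will be comparison of changes from baseline to follow-up time points between groups". The time points are plural, and the sentence refers back to the general approach at the start of 9.6.
- **Method (9.6).** That general approach lists "t-tests and multiple regression for comparing continuous variables between groups". It does not choose between them and names no covariate. Mixed models are secondary, apart from a possible use for missing data. Intent-to-treat is the principal analysis.
- **Times (9.5.1).** "This outcome will be measured at baseline, mid-intervention (approximately weeks 7, 13, and 19) and at final follow-up/end of study (week 26"). None is called primary. Section 6.2.4 also lists the craving EMA among the 3- and 6-month follow-up assessments.
- **Stratum (9.2).** Randomisation uses blocks, "stratifying by BMI (above and below BMI of 25"). Section 9.6 does not mention BMI.
- **Sidedness (9.2).** For the same between-arm comparison, power is given as 80% two-tailed. The text then adds "we believe that a one-sided test, corresponding the hypothesis that the Ed+MBI group will have a greater effect" and quotes 88%.

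**The concern.** Two things are at stake.

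The first is precision. A t-test on change subtracts the whole baseline value. Regression subtracts only the part that predicts follow-up, so in large samples its variance is never the larger. Section 9.6 allows a regression but does not commit to one, and names neither baseline nor BMI stratum as a term in it.

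The second is error control. Either model, fixed in advance at one time, holds its nominal level. With model, time and sidedness all unstated, a reader of the results could not tell whether the reported comparison was chosen before or after the data were seen.

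**Working it through.** **Inputs from 9.2.** 30 per arm; baseline 50% of days (SD 11); follow-up 30% against 20% of days, a difference of 10 points with SD 11. The text does not say whether the second SD is that of change or of the follow-up value. The baseline to follow-up correlation rho is not given; I assume .3, .5 and .7.

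**1. The plan's own power figure.** Standard error = 11 × sqrt(2/30) = 2.84; 10/2.84 = 3.52. A two-sided t-test at 5% with 58 df then has 93% power if 11 is the SD of change. The plan states 80%, so the figure does not reproduce. That is a separate matter. Here it means that these inputs show no power shortfall from leaving out adjustment.

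**2. Precision.** Let k = baseline SD / follow-up SD.
- Variance of raw change is proportional to k² + 1 − 2·rho·k.
- Variance of the adjusted comparison is proportional to 1 − rho².
- Ratio = (k² + 1 − 2·rho·k)/(1 − rho²) = 1 + (k − rho)²/(1 − rho²), which is never below 1.
- At k = 1 this reduces to 2/(1 + rho).

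| k | rho .3 | rho .5 | rho .7 |
|---|---|---|---|
| 0.5 | 1.04 | 1.00 | 1.08 |
| 1 | 1.54 | 1.33 | 1.18 |
| 1.5 | 2.58 | 2.33 | 2.25 |

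If 11 is instead the SD of the value at both times (k = 1), the SD of change is 11 × sqrt(2(1 − rho)) = 13.0, 11.0 and 8.5. Power is then .83, .93 and .99 for raw change, against .95, .98 and .998 for the adjusted comparison. The gain from the BMI stratum cannot be sized from the documents.

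**3. Error if the choice follows the results.** Simulation with no arm effect, 30 per arm, normal outcomes, equal correlations between times, two-sided 5%:

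| What is left open | rho .3 | rho .5 | rho .7 |
|---|---|---|---|
| Nothing: change t-test | 5.0% | 5.0% | 5.0% |
| Nothing: adjusted regression | 5.0% | 5.0% | 4.9% |
| Model, at one time | 7.8% | 7.3% | 6.7% |
| Better of 2 times, adjusted model | 9.8% | 9.6% | 9.3% |
| Best of 4 times, adjusted model | 17.5% | 17.0% | 16.7% |

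With first-order autoregressive correlations, the last row is 18.0%, 16.9% and 15.3%. Model choice alone at one-sided 5% gives 7.4%, 7.1% and 6.6%.

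**The case against.** The plan is less open than a quick reading suggests, and most of the case on the other side stands.

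- A reader might infer that baseline is ignored. It is not: 9.6 fixes the contrast as change from baseline, in the intent-to-treat population. A plain reading is a t-test on change, which holds 5%. Only regression adjustment is unsecured.
- A reader might infer that the trial will run at 17% error, or at the 22-25% that simulation gives when model and all four times are both open. The documents do not support this. They leave the choice unstated and nowhere say that the best result will be claimed. The plural in 9.6 covers every mechanism measure, and the tasks and questionnaires are followed up at 3 and 6 months, so a plural is needed for them anyway. Since 6.2.4 places EMA at those same visits, two follow-ups is a fair reading, and 17% is an upper figure for time choice under a fixed model.
- A reader might infer that R61 is underpowered without adjustment. On the inputs in 9.2, with 11 as the SD of change, it is not.
- R61 is a screening phase. Section 9.2 puts the within-arm decrease in Ed+MBI first and adds the between-arm test after it, so strict error control matters less here. Still, 9.6 calls the between-group comparison primary and gives no separate model for R33.
- The simulations assume normal outcomes. The EMA measure rests on at most nine prompts (three a day for three days) per period, so it is coarse and bounded, and the error rates are approximate.

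**Conclusion.** The concern holds as a low-cost improvement, not as a demonstrated error. Sections 9.6, 9.5.1 and 9.2 together leave the primary between-arm comparison without a named model, covariates, time or sidedness. The precision gain from adjustment is substantial if the SDs are similar and close to nil if the baseline SD is about half the follow-up SD; it rests on a correlation and an SD ratio that the documents do not give. The error figures apply only if the choice is made after seeing results. They are for R61 with 30 per arm; R33, with 120 people at 1:2, is not quantified. Error control and a clearly defined comparison are stronger reasons to act than power.

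**What to change.** In 9.6, name as the primary between-arm analysis a regression of the EMA craving-eating value, at one pre-stated time from 9.5.1, on arm, baseline EMA value and BMI stratum, in all randomised participants. State whether the test is one- or two-sided, and bring 9.2 into line. Label the change-score t-test and the other times as secondary.

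The cost is wording and two of 58 degrees of freedom. Baseline EMA and BMI stratum are already collected before randomisation. The real concession is that the team must commit to one time and gives up claiming success on the primary comparison at another.

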1. Determine if our EMA measures of behavioral mechanisms have high response rates (> 90%) and are ready for R33 use.
2. Determine if there is preliminary evidence that the MBI intervention impacts our hypothesized mechanisms of action and that the proposed mechanisms predict improved dietary adherence.
3. Assess feasibility and acceptability of two intensities of maintenance (monthly group meetings alone or supplemented by individualized attention) to ensure they are ready for R33 testing.

R33 Specific Aims: We will randomize 120 persons with diabetes in a 1:2 ratio to the Ed (n=40) vs. Ed+MBI (n=80) arms and follow them for 12 months. After the 12-week intervention, we will observe participant for 8 weeks and then re-randomize them using an adaptive intervention design to receive further observation, light maintenance training, or intensive maintenance training, depending on level of adherence achieved during the observation period. We will address the following specific aims:

1. Test whether our proposed behavioral mechanisms (decreased eating in response to cravings or difficult emotions) predict dietary adherence.
2. Test the hypothesis that the Ed+MBI arm will have better dietary adherence than the Ed arm.
3. Compare randomized arms in the adaptive maintenance intervention design to optimize maintenance phase dosing in future trials.
4. Obtain preliminary assessment of intervention effects on clinical outcomes

Design and Outcomes

This is a two-phase study. Both phases will use a randomized, controlled trial design. After pilot testing in the first phase, the second phase will include employing an adaptive intervention design in the post-treatment phase to test optimization of the maintenance intervention (i.e. assigning maintenance intensity/dose based on how a participant is doing).

Interventions and Duration

Participants will attend 12-weekly study intervention classes based on their random assignment: either Education alone (Ed) or Education+Mindfulness (Ed+MBI). Both groups will learn and follow a CR diet, and will participate in maintenance phase activities. If assigned to Ed+MBI, they will also learn and practice mindfulness-based skills.

Sample Size and Population

Target sample size: 180 total (60 participants in the first/R61 phase, 120 in the second/R33 phase).

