6.2.4 Follow-up visits and other data collection

Follow-up assessments at 3 and 6 months include the following (all described above in the baseline assessment section):

- Blood draws/laboratory tests
- Weight measurement
- Computerized tests of behavioral impulsivity and cognitive tasks
- Health history/medication changes
- Online battery of self-report questionnaires; may be completed at in-person visit if preferred (described above)
- 24-hour dietary recall
- Craving EMA

We aim to complete the 3 and 6 month visits with all participants within a 2-3 week window at these timepoints.

At-Home Ketone Monitoring: Participants will be given a home ketone monitoring device (Precision Xtra® System) and ketone strips, which measure beta-hydroxybutyrate. This is a glucometer device that also measures ketones from finger-stick blood if ketone strips are inserted instead of glucose

strips. The device store data, which will be checked periodically during class sessions to confirm accuracy of self-reported measurements. *Frequency:* Participants will be asked to measure ketones before dinner 3 times a week for approximately 4 weeks during the intervention (to provide more intensively self-monitoring when starting the diet) and twice weekly thereafter to monitor ketosis/diet adherence. We will use the EMA system to send requests to check ketone levels and report values back. During study visits, participants will be asked to bring in the meter and staff will download data on devices to provide a check on accuracy of participant reported measures.

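### Ketone adherence is scored on the readings obtained, so tests skipped when off the diet inflate it, and skipping that differs by arm would create a false arm difference

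*Combined protocol and SAP*

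**What the plan says.** Section 9.6 (Data Analyses) measures dietary adherence in two ways: the "proportion of blood ketone measures" at or above 0.3 mmol/L, and the "proportion of kcal from carbohydrate, using 24-hour diet recall". Each is related to the mechanism measures by linear regression. No section makes requested readings the denominator, or gives an averaging window, a minimum number of readings, a weighting by week, or a rule for a test that was not done.

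Section 6.2.4 asks participants to test "before dinner 3 times a week for approximately 4 weeks during the intervention" and then "twice weekly thereafter to monitor ketosis/diet adherence". The schedule is the same in both arms. On prompting and checking it says "We will use the EMA system to send requests to check ketone levels and report values back", and that at study visits "staff will download data on devices to provide a check on accuracy of participant reported measures". Section 3 states that neither participants nor staff are blinded.

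For missing data, section 9.6 offers mixed-effects models and multiple imputation if the amount is still substantial. It also plans secondary mixed models with linear splines for repeated measures.

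In the Précis, R33 Aim 2 is to "Test the hypothesis that the Ed+MBI arm will have better dietary adherence than the Ed arm".

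**The concern.** A proportion of the readings obtained estimates adherence only if the chance of doing the test does not depend on whether the person is on the diet. A prompted finger-stick at home can be skipped, and a participant who knows the reading will be low has a reason to skip it. Each such skip removes a non-adherent reading from numerator and denominator alike, and the proportion rises.

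If both arms skip alike, the level is inflated but a comparison under no true difference remains valid. If they skip differently, the comparison is biased. Differential skipping is plausible here. The trial is unblinded, and section 5.2 gives Ed+MBI an extra weekly hour and an app. The direction cannot be foreseen: more contact could raise testing in that arm on off-diet days, or change testing in some other way.

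Section 2.2 presents ketones as a biomarker for comparing the two approaches, so comparability between arms is the property that matters. At stake are the ketone version of R33 Aim 2 and the regressions that use the ketone measure. The planned statistic would not reveal the problem, because a ratio of completed readings does not look incomplete.

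A second, smaller matter is weighting. If readings are pooled over a period that spans the change in test frequency, the early weeks count for more than their share of time.

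**Working it through.** **What there is to reproduce.** The documents give no figure for ketone-test completion, for expected ketone adherence, or for an arm difference on it. Every completion rate below is an assumption. The test schedule and sample sizes come from the documents.

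**Skipping.** Let p be true adherence, a the share of requested tests done on adherent days, and b the share done on off-diet days. Then

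observed share = p·a / (p·a + (1 − p)·b).

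With p = 0.50 and a = 0.90:

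| b | Observed share |
|---|---|
| 0.90 | 0.45/0.90 = 50.0% |
| 0.80 | 0.45/0.85 = 52.9% |
| 0.70 | 0.45/0.80 = 56.3% |
| 0.60 | 0.45/0.75 = 60.0% |
| 0.50 | 0.45/0.70 = 64.3% |

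With true adherence equal in the arms, the false difference is:
- 80% against 70% off-diet completion: 56.3 − 52.9, about 3 points;
- 80% against 50%: 64.3 − 52.9, about 11 points;
- equal completion: zero.

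Swapping the arms reverses the sign.

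**Effect on a test.** A simulation of t-tests at two-sided 0.05 assumed mean true adherence 0.60 in both arms, between-person SD 0.20, 28 requested readings per person and 0.90 completion on adherent days. None of these except the 28 readings follows from the documents.

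| Phase (Ed vs Ed+MBI) | Off-diet completion, Ed vs Ed+MBI | False difference | False rejection |
|---|---|---|---|
| R61 (30 vs 30) | 0.6 vs 0.6 | 0 | 4.8% |
| R61 | 0.8 vs 0.6 | +5.4 points | 16% |
| R61 | 0.9 vs 0.6 | +8.0 points | 30% |
| R33 (40 vs 80) | 0.8 vs 0.6 | +5.6 points | 26% |
| R33 | 0.9 vs 0.6 | +7.8 points | 45% |

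**Early weighting.** Weeks 1 to 4 request 4 × 3 = 12 readings.
- Over 12 weeks the total is 12 + 8 × 2 = 28, so the early weeks supply 12/28 = 43% of readings in 4/12 = 33% of the time.
- Over 26 weeks the total is 12 + 22 × 2 = 56, so they supply 12/56 = 21% in 4/26 = 15% of the time.

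These are weights, not biases. To see a bias, take one arm at 0.90 in weeks 1 to 4 and 0.45 in weeks 5 to 12. Its time average is (4 × 0.90 + 8 × 0.45)/12 = 0.60, but its pooled score is (12 × 0.90 + 16 × 0.45)/28 = 0.643. Against an arm flat at 0.60, that is a 4.3-point shift. If week-by-week adherence is the same in both arms, the shift is zero. Averaging weekly proportions with equal weight returns 0.60.

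**Does counting missed tests as below 0.3 bound the arm difference?** The score then becomes p·a. With p = 0.50 in both arms and on-diet completion of 95% against 80%, it is 47.5% against 40%, a false 7.5 points. It removes the false difference only when on-diet completion is equal between arms.

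Opposite extremes do bound the difference. In the example with b = 0.80 and b = 0.50, the missed shares are 1 − 0.85 = 0.15 and 1 − 0.70 = 0.30, and 0.45 of requested readings are observed adherent in each arm. The ranges are 0.45 to 0.60 and 0.45 to 0.75. The difference (second arm minus first) therefore lies between 0.45 − 0.60 = −15 points and 0.75 − 0.45 = +30 points. The true zero is inside, but the interval is wide.

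**The case against.** The plan is not without safeguards. Tests are prompted, meters are checked in class and downloaded at visits, imputation is available, and the spline mixed models could absorb uneven timing if fitted to single readings. Adherence is also measured by a 24-hour recall taken without notice (section 6.2.2), which finger-stick skipping cannot touch. In R61, adherence is a secondary outcome, and section 9.2 calls the mechanism correlations of lesser concern at that stage.

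Much of this stands, and it limits the point. It does not remove it. Prompts do not ensure tests, and a download cannot recover a test never done. Standard mixed models and imputation assume missing at random, which fails when people skip because they are off the diet. Section 9.6 relates the proportion, not single readings, to the mechanisms.

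Four stronger readings are tempting and are not supported:
- A reader might infer that heavier early testing by itself creates an arm difference. The schedule is common to both arms, so it does so only if time courses differ and readings are pooled across the frequency change. Section 9.6 gives no window, and section 6.1 also lists ketone monitoring at the 3- and 6-month follow-ups. A window around those visits would contain only twice-weekly readings.
- A reader might infer that every mechanism regression is affected. Those on 24-hour recall are not, and R33 Aim 2 speaks of dietary adherence, not of ketones alone.
- A reader might infer that skipping will occur, or will favour Ed+MBI. The documents hold no data on either.
- A reader might take scoring missed tests as non-adherent to be conservative. It is so for the level, but not for the arm contrast, as the 7.5-point example shows.

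**Conclusion.** The point holds as a statement of what the rule permits. As written, the ketone proportion is inflated if participants skip tests when off the diet. It yields a false arm difference, of either sign, if that skipping differs between arms. Under the stated assumptions the difference runs from zero with equal skipping, through about 3 points at 80% against 70% off-diet completion, to about 11 points at 80% against 50%. Its real size and direction are unknown until completion is reported.

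Uneven test frequency is a separate and smaller matter: 4.3 points in the steepest 12-week case tried, and nothing when the arms share a time course. The consequences are confined to the ketone measure, in R33 Aim 2 and in the regressions that use it. This is a cheap improvement worth making before R33 data are analysed, not a flaw that undermines the trial.

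**What to change.** Amend section 9.6 as follows.

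1. State the window for ketone adherence. Score it per week and average weeks equally, or use a reading-level mixed logistic model with week. This corrects uneven timing only; it does nothing for skipping.
2. Report completed over requested readings by arm and week.
3. Prespecify one sensitivity analysis for missed requested readings. It should count them as below 0.3 mmol/L in both arms, and should also vary the assumed adherent share of missed readings separately by arm, as a tipping-point analysis that includes the opposite extremes. The same-direction version alone does not bound the arm difference.
4. Use meter downloads in preference to self-reported values where both exist.

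The cost is wording and modest extra analysis. The test schedule fixes the number of requested readings and the meters are already downloaded, so no new data collection is needed. The downside is that the extreme bounds may be wide, as the −15 to +30 point example shows. They should be labelled as sensitivity limits, not as the main estimate.
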